20.1 Appendix 1 – Amendment History

Amendment No.	Protocol version no.	Date issued	Author(s) of changes	Details of changes made
SA1	2.0	01 May 2018	[name] [name]	
1.Revised recruitment strategy to enable recruitment of eligible patients referred directly to [name], or who contact the study team.2.Amended age of diagnosis to ≤24 months3.Allow collection of RNAseq sample at visits for Study 1 and Study 2. Therefore, in Study 2, parents will not collect fingerprick samples for RNA analyses.4.Where venepuncture is difficult, participants will be offered the option of another visit or collecting a fingerprick sample and posting it to Exeter (for analysis of HbA1c, C-peptide, autoantibodies and DNA), or to withdraw from the study.
SA3	3.0	01 November 2019	[name] [name]	
1.Allow additional visit for a small subset of Study 1 participants.2.Updated information sheets and consent forms to provide greater clarity that some participants may not have developed diabetes yet, or may be invited for a second visit, or may be offered a home fingerprick sampling method instead of a face-to-face visit. NIHR branding has also been updated.
1617-23-SA-08	4.0	01 March 2022	[name] [name]	
1.Updated protocol for Phase 2, to include addition of non-diabetic controls cohort.2.New activities added for Guy's & St Thomas' NHS FT and Royal Devon University Healthcare FT, to recruit non-diabetic controls cohort.

				3. New participant information sheet and consent form for parents of non-diabetic controls. 4. Minor edits to study participant information sheets and consent forms to make up-to-date for Phase 2.
1617-23-A12	5.0	24 November 2022	[name] [name]	1. Protocol and information sheets (studies 1 & 2) updated to remove home visit as an option, and to indicate that the research visit may be arranged separately if it cannot be combined with review visit. 2. Consent and Assent forms (studies 1 & 2) updated to refer to new PIS version.
1617-23-SA4	6.0	17 July 2024	[name] [name]	1. Protocol updated to indicate study extension to 30/11/2025 and increased recruitment total from 240 to at least 260, mainly by increasing the healthy control cohort as described.
1617-23-S-A20	7.0	24 November 2025	[name] [name]	1. Protocol updated to indicate Phase 3 funding award and study extension to 30/11/2028, plus increased recruitment total to at least 300.

20.2 Appendix 2 – Study 1: Confirmation of EET1D as an autoimmune disease leading to beta-cell destruction

This study aims to assess autoimmunity and beta-cell function. Since most patients live outside Exeter, small blood volumes (as taken from very young subjects) and robust techniques will be required because samples will need to survive being sent to Exeter by courier.

Assessment of Autoimmunity

- Autoantibodies:** To establish whether EET1D is an islet specific B-cell autoimmune disease, we will test serum/plasma from >50 EET1D patients for islet autoantibodies (GAD, IA-2 and ZnT8) in Exeter (established assays, part of international QA scheme lead [name]) and also duration-matched T1D controls.

Islet specific autoreactive T cells in EET1D (visiting Lab of [name], Leiden University Medical Center, Netherlands). We will collect peripheral lymphocytes (PBMCs) for assessment of autoreactive CD8 T cells samples from >20 UK patients with EET1D, duration-matched T1D controls and age/duration-matched monogenic non-autoimmune diabetes. We may send the participants' PBMCs to [name] to investigate the presence and specificities of islet-specific CD8 T cells using the Diab-Q-kit developed by [name]. The QDot analyses require only 2 million cryopreserved PBMCs and has separated T1D from non-T1D in numerous settings(5-7), making it an ideal assay to assess autoimmunity in EET1D. We will determine the frequencies of islet-specific CD8 T cells against insulin B10-18, PPI15-24, IA-2797-805, GAD65114-123, GRP265-273 and pPIAPP5-13.using peptide-MHC multimers labelled with Qdots. We will compare the activation status of the islet-specific CD8 T cells by flow cytometry. Cells will be analysed for the expression of markers involved in effector activation and memory states (CCR7/CD45RA) and capacity to migrate to the inflamed pancreas (CXCR3)(14,15).With this analysis, we aim to elucidate whether islet-specific CD8 T cells from EET1D patients express an immune signature consistent with autoimmune T1D and how it varies from T1D with a normal onset. Through additional funding from The Leona M. and Harry B. Helmsley Charitable Trust, this study now includes additional analysis of CD4 T cells by [name] (King's College London).

- Assessment of loss of beta-cell function:** We will assess the loss of endogenous beta-cell function in >50 EET1D patients and controls by measuring C-peptide in parallel with the autoantibody measurement. C-peptide will be taken in EDTA plasma which allows it to be stable

for 24 hours in whole blood at room temperature(12). A non-fasting random post-meal sample has been shown to be a sensitive and specific measure of insulin deficiency without the need for omission of insulin or a formal stimulation test(16).

- iii) **Outcome:** The focus of study 1 is to establish evidence that the EET1D patients have features of islet-specific autoimmune diabetes that through beta-cell destruction causes progression to severe insulin deficiency (and whether this process differs from T1D at a later age of diagnosis).

20.3 Appendix 3 – Study 2: Investigation of mechanisms of EET1D

In this second study, we will examine for mechanisms that can explain the very early onset of islet-specific autoimmunity in EET1D. This will involve looking for differences in genetics, maternal genetics, intra-uterine environment, and autoimmune function.

Genetic analysis

- i) **HLA high resolution sequencing:** we aim to define HLA to 6-digit definition by sequencing the entire 3.8Mb HLA region using a combination of CATCH-seq targeted capture with Pacific Biosciences sequencing in 100 patients with EET1D and 100 T1D patients (diagnosed 1-10 years) matched for 2 digit HLA genotype (DR3/DR4 haplotype combinations). The Pacific Biosciences technology provides an opportunity to fully interrogate the HLA region in these patients using long-read sequencing that avoids the difficulties of haplotyping with shorter read approaches(17). The Exeter group has extensive experience of analysing PacBio data (having been recently awarded a £1m MRC clinical infrastructure grant for the PacBio sequencing machine and associated computing). We will use the PacBio SMRT portal for analyses including de-multiplexing, generation of haplotypes, read alignment and variant calling. We will look for differences in frequencies of rare or novel risk variants between EET1D and T1D. For example, we will have 80% power to detect a rare variant that is present in 0.1% of controls, but >15% of cases at a $P<0.0005$.
- ii) **Maternal genetic factors: Non-inherited maternal allele (NIMA) and microchimerism analysis.**
We will assess whether non-inherited maternal alleles (NIMA) are important in EET1D. Non-inherited maternal HLA alleles that are associated with no/reduced risk for T1D can increase the likelihood of T1D in offspring(18). We have parental DNA from 100 EET1D cases so we can test if the NIMA of mothers of EET1D are more likely than by chance to be non-DR3 and non-DR4 (comparing to paternal HLA) and whether at non-HLA loci the NIMA are more likely to be protective alleles than expected by chance. Maternal DNA (microchimerism-presence of maternal cells in the offspring) is measurable in T1D at higher proportions than in controls and non-diabetic siblings in the peripheral blood and pancreas of patients with T1D. We will use assays developed by [name] (University of Bristol)(9) to assess the presence of maternal microchimerism in fetal circulation in EET1D compared to NDM and T1D (diagnosed 1-10 years).
- iii) **Longitudinal analysis of Immune Phenotype:** The initiation of autoimmunity in T1D has been very difficult to characterize due to uncertainty regarding when the process starts. The identification of EET1D patients so close to birth allows a unique opportunity to study T1D very close to the initiation of autoimmunity. We will study autoimmunity in newly referred patients with EET1D (n=20) and NDM (age-matched controls n=20) at diagnosis and after 2 years follow up and assess autoimmunity using 3 methods that can all be performed in early life due to the small samples required:
 - a) Islet autoantibody measurement
 - b) QDot analysis for CD8 T cells
 - c) T1D-specific transcriptomic analysis using RNA sequencing (8). This last analysis is in collaboration with [name], (Benaroya Research Institute). The key outcome will be to assess which markers of autoimmunity are present at diagnosis and how they change at 2 years follow-up. It has never previously been possible to study T1D that has occurred in such a short space of time after birth and this offers the possibility to identify the first immune signature of the disease.

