- i) To compare genetic and functional markers of autoimmunity in EET1D to T1D and NDM.
- ii) To develop a robust pathway to identify, recruit and study early-onset diabetes for a prospective protocol for future study and assessment of patients close to diagnosis of diabetes.

Primary Endpoint/Outcome

Serum/urine C-peptide and autoantibodies (IAA, GAD, IA-2, ZnT8) in EET1D compared to T1D and NDM.

Secondary Endpoints/Outcomes

- i) Prevalence and frequency of islet specific CD8 T cells in EET1D compared to T1D, NDM(5-7) and controls.
- ii) Frequency and phenotype of pro-inflammatory and regulatory T cells in EET1D compared to T1D, NDM and controls.
- iii) Difference in immune gene expression, as measured by RNAseq in newly diagnosed EET1D v NDM and v controls(8).
- iv) Association of maternal and paternal non-inherited HLA alleles with EET1D v older onset T1D and NDM(9).

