- ii) We have now thoroughly reviewed patients already referred to the Exeter team and anticipate fewer newly recruited patients from this cohort than originally predicted (e.g. due to death or out of date contact details). We have been approached by eligible patients directly and, with new referrals from clinicians, these may make up for this shortfall, so alternative referral methods will be permitted. Additionally, the rarity of this condition means predictions of recruitment are very difficult, as are power calculations for the proposed analyses. We plan to recruit as per this updated protocol (and the new recruitment routes) and then may propose revised recruitment targets in 12 months based on these altered recruitment strategies.
- iii) attempt to recruit healthy non-diabetic children as controls for Studies 1 and 2. Option 1 is to recruit healthy children when attending elective surgery at specified participating sites, as described above. As a second option, if recruitment proves slower than anticipated, we would recruit children with congenital non-immune thyroid disease when they attend paediatric clinic for blood draw (~5 times in the first year of their life), giving an opportunity for a sample to be collected for functional immune analysis. The recruitment priority will be children aged under 2 years but eligibility will be 0 to age 6 years.

Patients for study and controls (Studies 1 and 2)

Defining patients as EET1D:

Patients will be selected on the basis of:

- i) diagnosis of diabetes <24 months (with continued primary focus on recruitment of those diagnosed <12months)
- ii) exclusion of mutation in all 23 monogenic non-autoimmune neonatal diabetes genes using targeted capture Next Generation Sequencing(NGS) if diagnosed <12 months (3)
- iii) T1D GRS within distribution of T1D reference population(10).
- iv) Diagnosis of monogenic type 1 diabetes defined as a mutation in a gene known to cause type 1 diabetes (e.g. *FOXP3* and *STAT3*) or a Down's syndrome (added with additional funding for recruitment and analysis from The Leona M. and Harry B. Helmsley Charitable Trust).

Study 1: existing cases of any age meeting above criteria.

Study 2: new cases referred to Exeter Genetics Service or [name] within 12 months of diagnosis, meeting above criteria, and aged <24 months.

Comparison groups:

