4.2 Inclusion Criteria

Study 1:

EET1D

- Aged 0 to 70 years
- Clinical diagnosis of diabetes or autoimmunity <24 months (+ evidence of WHO diabetes criteria)

T1D Controls

- Age 0-70 years (matched to above)
- Clinical diagnosis of T1D (diagnosed age 2-20 years)
- Insulin treated from diagnosis.

Monogenic / NDM controls

- Diagnosis of diabetes <12 months
- Diagnosis of monogenic / NDM (confirmed by Exeter Molecular Genetics Laboratory).

Study 2:

EET1D

- Aged 0 to 24 months at recruitment
- Clinical diagnosis of diabetes <24 months (+ evidence of WHO diabetes criteria); recruited within 12 months of diagnosis.
- Negative genetic test for mutations causing non-autoimmune neonatal diabetes
- Type 1 diabetes genetic risk score >50th centile of T1D reference group, or monogenic cause of T1D (e.g. *STAT3* or *FOXP3* mutation)

NDM controls

- Diagnosis of diabetes <12 months
- Diagnosis of NDM (confirmed by Exeter Molecular Genetics Laboratory).

Non-diabetic controls for Studies 1 and 2:

- Aged 0-6 years (The recruitment priority will be children aged under 2 years but to include children aged 2-6 years)
- Attending specified participating hospital sites for elective surgery, including but not limited to: inguinal hernia repair, umbilical/midline hernia repair, orchidopexy, gastrostomy insertion/change, hypospadias repair, cleft palate repair, excision of accessory digit, laryngoscopy, adenoidectomy, tonsillectomy, MRI under general anaesthesia, eye surgery.

Should recruitment be slower than anticipated, we would recruit children with congenital non-immune thyroid disease when they attend paediatric clinic for blood draw.

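### At non-HLA loci, Appendix 3 tests non-inherited maternal alleles only against chance; if that means 50:50 transmission, the child's own inherited risk reads as a maternal effect

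*Protocol*

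**What the plan says.** Appendix 3 (section 20.3), under maternal genetic factors, sets out the aim: "We will assess whether non-inherited maternal alleles (NIMA) are important in EET1D". The material is described as follows: "We have parental DNA from 100 EET1D cases". Two tests are then stated.

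- **HLA:** whether the NIMA are "more likely than by chance to be non-DR3 and non-DR4 (comparing to paternal HLA"). It does not say whether this means the father's inherited alleles, his non-inherited alleles or both.
- **Non-HLA loci:** "whether at non-HLA loci the NIMA are more likely to be protective alleles than expected by chance". Chance is not defined and no parental comparator is given.

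Secondary endpoint (iv) in section 3.2 words the HLA comparison more exactly: "Association of maternal and paternal non-inherited HLA alleles with EET1D v older onset T1D and NDM(9"). It does not mention non-HLA loci.

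Two passages bear on how the cases were selected. The EET1D definition in section 4.1 includes "T1D GRS within distribution of T1D reference population(10"). The Study 2 criteria in section 4.2 require "Type 1 diabetes genetic risk score >50th centile of T1D reference group, or monogenic cause of T1D". No significance level, number of loci, pooling rule or effect size is given for the NIMA tests.

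**The concern.** The NIMA is the maternal allele that the child did not receive. In a heterozygous mother it is the protective allele exactly when the child received the risk allele. The families enter the study because the child is affected, and most polygenic cases must also have a T1D-like genetic risk score. At any true T1D locus, such children have received the risk allele more often than half the time. Measured against 50:50, the NIMA is then protective too often even if it does nothing. The test becomes a transmission test of the child's own risk alleles under another name.

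Study 2 looks for mechanisms of very early onset, and maternal genetics is one of those listed. A positive result from such a test could not separate a maternal mechanism from ordinary inherited risk.

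**Working it through.** The protocol gives no figure for these tests, so there is none to reproduce. The check asks how often each comparator rejects when there is no maternal effect.

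**Inputs.** 100 families (Appendix 3). Assumed, because the protocol gives none: risk-allele frequency p spread evenly over 0.2 to 0.6, per-allele odds ratio (OR) 1.1 to 2, random mating, and risk that depends only on the child's own genotype.

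**Step 1: the bias.** The transmitted allele is the risk allele with probability q = p·OR / (1 − p + p·OR). The non-transmitted allele is the risk allele with probability p. Among heterozygous mothers, the share whose NIMA is protective is

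s = q(1 − p) / [q(1 − p) + (1 − q)p] = OR / (1 + OR).

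This gives 52.4% at OR 1.1, 54.5% at 1.2, 56.5% at 1.3 and 66.7% at 2, against 50%.

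**Step 2: false rejection against 50:50.** The number of informative mothers is n = 100 × loci × average of [q(1 − p) + (1 − q)p]. Rejection in the NIMA direction (z > 1.96, nominal 2.5%) is 1 − Φ{[0.98 − (s − 0.5)√n] / √(s(1 − s))}.

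| Loci | OR | n | Calculation | Rejection |
|---|---|---|---|---|
| 1 | 1.1 | 45.7 | (0.98 − 0.161)/0.499 = 1.64 | 5% |
| 1 | 1.3 | 46.4 | (0.98 − 0.444)/0.496 = 1.08 | 14% |
| 1 | 2.0 | 48.5 | (0.98 − 1.160)/0.471 = −0.38 | 65% |
| 10 | 1.2 | 461 | (0.98 − 0.976)/0.498 = 0.01 | 50% |
| 30 | 1.10 | 1,371 | (0.98 − 0.882)/0.499 = 0.20 | 42% |
| 30 | 1.15 | 1,377 | (0.98 − 1.294)/0.499 = −0.63 | 74% |
| 30 | 1.20 | 1,382 | (0.98 − 1.690)/0.498 = −1.43 | 92% |

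Simulation of the same scenarios agrees to within about one percentage point.

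**Step 3: the other comparators at non-HLA loci.** Non-transmitted alleles keep their population frequency when risk depends only on the child's genotype. A test against the true population frequency therefore stays near its level: 4.8% to 6.6% in simulation, nominal 5% two-sided, including HLA-like loci. NIMA against NIPA, paired within family, rejects 4.8% to 5.5% over the scenarios in the table.

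**Step 4: HLA.** Suppose transmitted haplotypes carry DR3/DR4 in a proportion t of 60% to 85%, and non-transmitted ones in a proportion u of 30% to 35% (assumed). The NIMA is non-DR3/DR4 with probability 1 − u. Over both paternal haplotypes the figure is 1 − (t + u)/2. A two-sided 5% test of 100 maternal against 200 paternal haplotypes gives:

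| t | u | NIMA | All paternal | Rejection |
|---|---|---|---|---|
| 60% | 35% | 65% | 52.5% | 55% |
| 60% | 30% | 70% | 55% | 72% |
| 85% | 35% | 65% | 40% | 99% |
| 85% | 30% | 70% | 42.5% | above 99% |

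Against the non-inherited paternal haplotype alone, rejection is about 5% in all four cases.

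**The case against.** The strongest reply is that the protocol never says 50:50, never mentions heterozygous mothers, and may leave the definition of chance to an analysis plan that is not shown. That stands, and it makes the point conditional. Under the population-frequency reading there is no over-transmission bias. That reading has its own requirement: section 4.1 describes referrals from 84 countries, with 40% of identified patients in the UK, so the reference would have to match the families' ancestry.

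A reader might also infer that the HLA test is biased as written, because the appendix says only paternal HLA. The documents do not support this. Endpoint (iv) names maternal and paternal non-inherited HLA alleles, so the appendix phrase is most naturally shorthand for the NIPA, which is a sound comparator. The Step 4 figures apply only if the transmitted paternal haplotype were included.

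The size depends on assumptions. At a single weak locus the bias is small. The large figures need a strong locus or pooling, and the protocol says neither how many loci there are nor whether they are pooled.

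The argument from risk-score selection should not be pressed. The criterion above the 50th centile applies to Study 2 and has a monogenic alternative, and the appendix does not say that the 100 families are those recruits. Ascertainment through an affected child is enough to cause the bias.

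Finally, the non-HLA test is not a listed endpoint, and the study was sized for feasibility. That limits the consequence. It is not a reason to keep a weaker comparator when a better one is already named for HLA.

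**Conclusion.** The point holds for non-HLA loci on one condition. If chance is Mendelian 50:50, which is the natural within-family reading, the stated test can report a maternal effect that is only the child's own inherited risk. False rejection against a nominal 2.5% runs from about 5% (one locus, OR 1.1) to 65% (one locus, OR 2), and from about 42% to 92% when 30 loci at OR 1.1 to 1.2 are pooled. These figures rest on 100 families, assumed allele frequencies and odds ratios, and random mating.

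It would go too far to say that the planned tests will produce a false maternal effect: a population-frequency null would not. For HLA the point is one of alignment between Appendix 3 and endpoint (iv), not a demonstrated fault. This is a worthwhile, inexpensive improvement to a secondary mechanistic analysis. It does not touch the primary outcome, recruitment or sampling.

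**What to change.** In Appendix 3, under maternal genetic factors:

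- **Non-HLA loci:** replace the comparison with chance by a paired comparison of NIMA with NIPA in the same EET1D families, restricted to families with both parents genotyped. Add that departure from 50:50 transmission will not be interpreted as a NIMA effect.
- **HLA:** change paternal HLA to non-inherited paternal HLA, so that the appendix matches secondary endpoint (iv).

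Only wording changes, since section 5.2 says parental DNA is already stored at referral. There are two costs. Families without paternal DNA drop out; the protocol does not say how many of the 100 have both parents. The contrast is also less precise than one against a fixed 50%, because both sides of it vary.

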Chief Investigator:

Signature:

A handwritten signature in black ink that appears to read '[name]'.

Date: 24/11/2025

Name: (please print): **[name]**

Position: Professor in Diabetes and Nephrology

STUDY SUMMARY/SYNOPSIS

Study Title	Understanding beta-cell destruction through the study of Extremely Early-onset Type 1 Diabetes (EET1D)
Short Title and Internal ref. no.	EXE-T1D CRF 228
Study Design	Retrospective observational and prospective observational cohorts
Lead Study Centre	Royal Devon University Healthcare NHS Foundation Trust
Study Summary	A study to assess clinical phenotype, beta cell function, genetics, and autoantibodies in EET1D and/or autoimmunity to better understand the aetiology and progression of beta cell destruction in T1D occurring in the first 2 years of life.
Study Participants	Study 1: Cross sectional study of existing and new cases of EET1D, diagnosed with T1D in the first year of life. Participants will be identified retrospectively and prospectively from referrals to the Exeter Molecular Genetic Laboratory or [name]. Study 2: Newly diagnosed cases of EET1D, again identified by referral to Exeter Molecular Genetics Laboratory or [name]. Age-matched cohort without diabetes: Children undergoing elective surgery/clinic will be recruited to collect samples for comparison of immunological development.
Planned Sample Size	Study 1: 100-130 EET1D and 100 controls Study 2: 40-60 EET1D and 10-40 controls Age-matched non-diabetic control cohort: 60-80
Treatment duration	Study 1: Single visit for sample collection (with possible 2 nd visit to confirm abnormal findings) Study 2: One/Two visits close to diagnosis, and approx 2 years later for some children (see Follow up duration) Age-matched non-diabetic control cohort: recruitment and sample collection during elective surgical procedure
Follow up duration	2 years (+/- 18 months) for some UK Study 2 participants recruited in Phase 1, or if required to confirm abnormal findings.
Planned Study Period	Phase 1: 01/09/2017 – 30/11/2021 Phase 2: 01/12/2021 – 30/11/2025 Phase 3: 01/12/2025 – 30/11/2028

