3.2 Study Aim

The EXE-T1D study will take people with T1D diagnosed before the age of 24 months and compare them to people with T1D diagnosed at more typical ages (1-20 years), and people diagnosed with non-autoimmune diabetes at a similar very young age (children with neonatal diabetes [NDM]), and infants without diabetes matched for age.

EXE-T1D is an observational study organised into two sub-studies:

Phase 1 aims:

Study 1: Cross-sectional study of existing patients with EET1D:

Aim: To compare clinical features, beta cell loss (measured by serum/urine C-peptide), islet-specific autoantibodies, T1D risk genes and autoreactive CD8 T cells in people already known to have EET1D and already referred to Exeter for genetic testing or directly to [name], to those people with T1D diagnosed at older ages (age 1-20 years).

Study 2: Study of newly referred patients:

Aim: To assess immune function (by measuring autoantibodies, autoreactive CD8 T cells and RNAseq of immune genes) at diagnosis and longitudinally in people with newly diagnosed EET1D compared to newly diagnosed monogenic neonatal diabetes.

Phase 1 recruitment:

Total recruited = 163: 137 to study 1, including 18 with fingerprick samples, and 24 to study 2. Numbers were affected by the COVID-19 pandemic and follow-up of UK study 2 patients is ongoing.

Phase 2 recruitment:

Total recruited = 267. To reflect the most valuable samples to date, we recruited 23 more patients with EET1D (reflecting incidence and referral rate), 1 monogenic / NDM control, 60 non-diabetic controls (age 0-6 years) and 20 newly diagnosed T1D controls. We prioritised recruitment to Study 2 (age <2 years). These patients are extremely rare and numbers are dependent on incidence and referrals so the above numbers reflect referral rates.

It is important to overlap recruitment of cases and controls to reduce risk of batch effects in immune and RNA analysis.

Phase 3 extension aims:

We will prioritise recruitment to Study 2 (age <2 years) plus age-matched non-diabetic controls and monogenic / NDM controls when identified. These patients are extremely rare and numbers are dependent on incidence and referrals so achieving the proposed targets depends on referral rates.

Primary Objective

The primary objective of the study is to compare beta cell function and islet autoantibodies in EET1D to T1D, NDM and non-diabetic controls.

Secondary Objectives

The secondary objectives of the study are:

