We will use a home sampling pack that allows collection of a blood sample from a fingerprick (for example, when the participant is testing their blood glucose from a fingerprick anyway) and post it (using prepaid postage packaging provided) to the Exeter Clinical Laboratories for analysis of HbA1c, C-peptide, autoantibody analysis and extraction of DNA. We will offer this option to individuals that meet Study 1 criteria but are of longer duration or cannot provide a standard EXE-T1D sample. Referred patients interested in the study will be sent the pack with study information sheet(s), consent form(s) and prepaid packaging. A telephone call will be arranged with the study research nurse and patient/parent/guardian to discuss the study, answer any questions, obtain informed consent and talk through the process of sample collection and posting to Exeter.

It is possible that, especially with young children, venepuncture during a study visit will not be successful (for example because insufficient blood draw is possible, or the infant is unwilling to have the blood draw). If this happens, we will offer the study participants the choice of another visit, the option to post a fingerprick blood sample, or to withdraw or not participate further in the study.

Example of blood volume used for research samples in infants:

WHO guidelines specify 1-5% of blood volume in one day. Children tend to have a blood volume of 75 ml/kg, so the limit would be 0.75 – 3.25 ml/kg. Therefore, for a child weighing 10 kg, the safe maximum, as advised by WHO, would be 7.5 – 32.5 ml.

Samples will be sent with 3 forms of identifiable information (name, DOB, NHS/CHI/hospital number) using Exeter-specific analyses request forms. The samples for C-peptide and autoantibodies will be tested in the Exeter Clinical Laboratory as clinical samples and results will be returned to the local clinical teams. Study results will be anonymised and stored by study ID on the study database. PBMC samples will be anonymised and cryopreserved.

Any travel costs related to the study will be reimbursed to study participants.

Study 2

In addition to the first visit, as detailed above, a repeat visit may be conducted two years (+/- 18 months) after Visit 1. We will not routinely perform a second study visit for participants recruited in phase 2 of the study, but, if we find major abnormalities, we may arrange a second sample to confirm findings.

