12.2 Feasibility

This is a study to establish infrastructure to study rare patients with EET1D and MT1D. The sample size has been selected to assess feasibility rather than on the basis of statistical power. In reality with these extremely rare but potentially very interesting patients, every single patient recruited could contribute on their own to a novel discovery. Whilst accepting that we do not know what immune, beta cell or autoantibody differences we are going to find, a group of 20 v 20 gives an 80% power (alpha 0.05) to detect a difference of 10% v 50% in a proportion between the two groups and a power of 85% (alpha 0.05) to detect a 1 SD difference in a continuous variable. Each case of EET1D included in the study increases the statistical power to find new immune and genetic associations. Sometimes individual cases have specific mutations which we are now funded to test for with whole genome sequencing. Additionally, to reduce the chances of batch effects in immune and other -omics analysis, we will continue to keep case recruitment open in parallel to recruitment to the non-diabetes control cohort.

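### Appendix 3 plans a 2-year comparison of 20 EET1D v 20 NDM children, a size that the routine second visits allowed elsewhere in the protocol cannot reach

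*Protocol*

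**What the plan says.** Appendix 3 iii (longitudinal analysis of immune phenotype) states the plan in the future tense: "We will study autoimmunity in newly referred patients with EET1D (n=20) and NDM (age-matched controls n=20) at diagnosis and after 2 years follow up". It then gives the aim of that analysis: "The key outcome will be to assess which markers of autoimmunity are present at diagnosis and how they change at 2 years follow-up".

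Other sections describe a narrower follow-up:

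- **Synopsis, Follow up duration:** "2 years (+/- 18 months) for some UK Study 2 participants recruited in Phase 1", or where abnormal findings need confirming.
- **Section 2:** the Phase 1 follow-up data are called sufficient, and Study 2 becomes a single-visit study for that reason.
- **Section 3.3:** some Study 2 children may give a second sample.
- **Section 5.2, Study 2:** "We will not routinely perform a second study visit for participants recruited in phase 2 of the study". A repeat may be arranged if major abnormalities are found.
- **Section 5.2, second sample:** for UK children recruited in Phase 1, the second sample is optional.
- **Section 3.2, Phase 1 recruitment:** "Total recruited = 163", made up of "137 to study 1, including 18 with fingerprick samples, and 24 to study 2". The same paragraph adds that "follow-up of UK study 2 patients is ongoing".
- **Section 3.2, Phase 2 recruitment:** 23 further EET1D patients and one monogenic/NDM control.

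The second visit is set at two years plus or minus 18 months after Visit 1.

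**The concern.** Appendix 3 gives a sample size for a two-timepoint comparison, while the visit schedule and the recruitment already reported imply a much smaller one. The appendix appears not to have been updated when Study 2 became a single-visit study.

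A reader of Appendix 3 would expect 20 pairs in each group and would judge any EET1D v NDM difference in change on that basis. With far fewer pairs, and possibly very few in the NDM group, a finding of no difference in change would say little, and an apparent difference would be imprecise. The size of the longitudinal component should be known before the results are read.

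The wide window adds a second, separate issue. A sample described as 2-year follow-up may have been taken at quite different intervals in different children.

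**Working it through.** **Inputs.** Pairs planned: 20 + 20 (Appendix 3 iii). Phase 1 total 163, of whom 137 in Study 1 and 24 in Study 2 (Section 3.2). Phase 2: 23 EET1D, 1 monogenic/NDM, 60 non-diabetic and 20 newly diagnosed T1D (Section 3.2). Window: 24 ± 18 months after Visit 1 (Section 5.2). Recruitment up to 12 months after diagnosis (Section 4.2). Power statement: 20 v 20, alpha 0.05 (Sections 12.2 and 12.3). A two-sided test is assumed, as the protocol does not say.

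**Step 1: head count.**
- Pairs needed: 20 + 20 = 40.
- Phase 1 recruits not assigned to either study: 163 − (137 + 24) = 2. Study 2 in Phase 1 is therefore 24, or at most 24 + 2 = 26.
- Phase 2 adds no routine pairs. Its total of 267 is cumulative (163 + 23 + 1 + 60 + 20 = 267), and only one of the additions is a monogenic/NDM control.
- Shortfall: 40 − 24 = 16, or 40 − 26 = 14. Both are minimums, because non-UK children and children not re-sampled have still to be removed.

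**Step 2: does any split work?** The EET1D/NDM split of the 24 is not reported. If 20 are in one group, the other has at most 24 − 20 = 4, or 26 − 20 = 6. No split gives 20 in both.

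**Step 3: the protocol's own 20 v 20 figures.** Sections 12.2 and 12.3 give 85% power for a 1 SD difference and 80% for 10% v 50%.
- Continuous: noncentral t with noncentrality d/√(1/n₁ + 1/n₂) = 1/√(1/20 + 1/20) = 3.16 on 38 degrees of freedom gives 86.9%.
- Binary: the pooled z test gives 81.3%.

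Both agree with the protocol to within 2 percentage points, so these figures are sound for 20 v 20.

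**Step 4: illustration at reachable sizes.** The same t calculation for a 1 SD difference between groups, with every Phase 1 Study 2 child re-sampled:

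| Split | Power |
|---|---|
| 20 v 20 (Appendix 3) | 86.9% |
| 13 v 13 (26 children) | 68.7% |
| 12 v 12 | 64.9% |
| 16 v 8 | 59.8% |
| 18 v 6 | 52.7% |
| 20 v 4 | 41.5% |

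At 12 v 12, 80% power needs a difference of 1.20 SD.

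**Step 5: timing.** 24 − 18 = 6 and 24 + 18 = 42, so the second sample falls 6 to 42 months after Visit 1. If Visit 1 is itself 12 months after diagnosis, the upper end is 42 + 12 = 54 months from diagnosis.

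**The case against.** The move to a single visit was deliberate and is explained in Section 2, and Section 3.2 lists the longitudinal aim under Phase 1. Section 12.2 says the sample size rests on feasibility rather than power. On this view Appendix 3 merely carries an outdated number in an observational study of a rare disease. Much of this stands, and it lowers the severity. It does not remove the conflict: Appendix 3 is current text, Section 2 gives no number of pairs, and calling the follow-up sufficient does not supply 20 per group.

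It could also be said that discretionary repeats might fill the gap. Section 5.2 allows them only after major abnormalities. Those children would be selected on the outcome under study, so they cannot properly make up either group.

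Three stronger readings are tempting, and the documents do not support them.

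- *That no longitudinal analysis is possible.* Sections 3.2, 3.3 and 5.2 all provide for second samples in some children, so a smaller subset can exist.
- *That the protocol claims 80% or 85% power for change.* The 20 v 20 figures in Sections 12.2 and 12.3 are general and are not tied to the longitudinal analysis. Appendix 3 states no power for change, and its key outcome can be read as description of change within children. The power figures above therefore only illustrate scale.
- *That samples at 6 and 42 months will be pooled as one visit, biasing the comparison.* The protocol sets a sampling window and does not say how time will be modelled. No difference in timing between the groups is shown. The window is also not a reason why 20 v 20 is out of reach.

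**Conclusion.** The point holds for the stated size. Twenty EET1D and 20 NDM children with paired samples cannot be obtained from the routine second visits the protocol allows: the ceiling is 24 pairs, or 26 at most, against 40. This does not depend on the unreported split.

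Two qualifications apply. The absence of a routine second visit is explicit for Phase 2; for Phase 3 it is inferred from the synopsis and Section 2. The power illustration assumes a two-sided test, a between-group comparison and re-sampling of every child, so 65% at 12 v 12 is the best case for 24 children.

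Severity is moderate. Change over 2 years is part of the key outcome of Appendix 3 iii but is not among the primary or secondary endpoints in Section 3.2, and the half of that key outcome concerning markers at diagnosis needs no second visit.

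**What to change.** 1. Reconcile the synopsis, Sections 2, 3.3 and 5.2, and Appendix 3 iii on who has a second sample, and say explicitly what applies in Phase 3.
2. In Appendix 3 iii, replace the two groups of 20 for the follow-up part with the actual number of paired samples per group, and give the precision or detectable difference that follows.
3. Label the EET1D v NDM comparison of change descriptive. Report repeats prompted by abnormal findings separately from routine second samples.
4. State in Sections 12.2 and 12.3 that the 20 v 20 power figures do not apply to change.
5. Report the interval between samples, and analyse change by actual elapsed time rather than as a fixed 2-year visit.

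The cost is mainly wording, plus a count of the pairs already collected. No extra sampling is required. The downside is a more modest longitudinal claim.
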